9.4.4 Analysis of Exploratory Objectives and Endpoints

Exploratory objectives and endpoints for immunophenotyping including transcriptomics, interferon-simulating gene analysis, proteomics, epigenetics, and T cell and innate immune cell phenotyping will be handled in a separate analysis plan. Samples for the exploratory objectives are outlined in this protocol and details of sample collection, processing, storage and shipping is described in detail the MOP, however, the analysis will not take place in real-time, during study enrollment. Depending on the timing of the completion of these assays, exploratory results will be submitted as one or more addenda to the primary CSR.

9.4.5 Safety Analyses

Safety endpoints include death through Day 29 (+ 6 days), SAEs and Grade 3 and 4 AEs. These events will be analyzed univariately and as a composite endpoint. Time-to-event methods will be used for death and the composite endpoint. Each AE will be counted once for a given subject and graded by severity and relationship to COVID-19 or study intervention. AEs will be coded using the current version of the Medical Dictionary for Regulatory Activities (MedDRA). AEs will be presented by system organ class, duration (in days), start- and stop-date. Adverse events leading to premature discontinuation from the study intervention and serious AEs will be presented either in a table or a listing.

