2.2.3 Subcutaneous Interferon beta-1a

2.2.3.1 Potential Risks of Subcutaneous Interferon beta-1a

Interferon beta-1a was first approved for licensure by the FDA in 1996 for intramuscular injection (AVONEX®); a subcutaneous injection was approved in 2002 (Rebif®). Interferon beta-1a is indicated for the treatment of patients with relapsing forms of multiple sclerosis and has been extensively studied in clinical trials (30, 31).

In a randomized, double-blind placebo-controlled trial, the most common adverse reactions among patients with relapsing multiple sclerosis who received 44 micrograms of subcutaneous interferon beta-1a three times per week for two years were depression, headache, influenza-like symptoms (e.g., fatigue, fever, rigors, chest pain, back pain, myalgia, arthralgia), abdominal pain, lymphadenopathy, leukopenia, transaminitis, and injection site reactogenicity. The most frequently reported adverse reactions resulting in clinical intervention (e.g., discontinuation of Rebif®, adjustment in dosage, or the need for concomitant medication to treat an adverse reaction) were injection site reactions, influenza-like symptoms, depression, and elevation of liver enzymes. The influenza-like symptoms typically last for about one day after injection, and the occurrence of

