7. STUDY INTERVENTION DISCONTINUATION AND SUBJECT DISCONTINUATION/WITHDRAWAL

7.1 Halting Criteria and Discontinuation of Study Intervention

7.1.1 Individual Study Product Halting

Study product administration for any given subject may be stopped for SAEs, clinically significant adverse events, severe laboratory abnormalities, or any other medical conditions that indicate to the Investigator that continued dosing is not in the best interest of the patient.

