8.3 Adverse Events and Serious Adverse Events

8.3.1 Definition of Adverse Event (AE)

AE means any untoward medical occurrence associated with the use of an intervention in humans, whether or not considered intervention related. If multiple abnormalities are part of the same clinical syndrome, they can be reported together as one AE under a unifying clinical diagnosis.

An AE can therefore be any unfavorable and unintended sign (including an abnormal laboratory finding), symptom, or disease temporally associated with the use of medicinal (investigational) product. Only Grade 3 and 4 AEs will be captured in this trial and Grade 2 or higher suspected drug-related hypersensitivity reactions associated with study product administration. For example, worsening respiratory status from Grade 2 (respiratory distress) at Day 1 to Grade 4 (respiratory failure) at Day 5 is a condition temporarily associated with use of an intervention and by definition is an AE and should be reported even if the investigator believes that this is part of the natural history of the disease.

All study required solicited safety laboratory test results will be recorded into the eCRF including all Grade 1 and 2 abnormalities. As the Grade 1 and 2 abnormalities are tracked and available within the data system, the Grade 1 and 2 laboratory abnormalities are not expected to be reported as adverse events and will not be reviewed by the clinical Monitor.

Given the severity of the underlying illness, subjects will have many symptoms and abnormalities in vital signs and laboratory values. As COVID-19 is an emerging, systemic disease involving not only the upper and lower respiratory tract, but also the gastrointestinal tract, cardiovascular system, endothelial cells, and central nervous system (olfactory neurons), it is important to document respiratory AE as well as AEs involving other systems. New symptoms not part of the subject's COVID-19 syndrome at Day 1, should be captured as adverse events. For example, if a subject develops new grade 3 gastrointestinal symptoms after Day 1, the gastrointestinal symptoms should be reported.

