8.3.5 Time Period and Frequency for Event Assessment and Follow-Up

For this study, all Grade 3 and 4 AEs, and all SAEs occurring from the time the first study product is initially given on Day 1 through the Day 29 visit will be documented, recorded, and reported.

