2.2.2 Remdesivir (Veklury®)

2.2.2.1 Potential Risks of Remdesivir

Remdesivir is an approved antiviral and may be obtained as part of standard care outside the clinical trial. For the purpose of the ACTT trials, remdesivir is still considered a study product being used as part of an investigational trial and it will be tracked and monitored accordingly.

Transaminase elevations have been observed in healthy volunteers who received remdesivir; the transaminase elevations were mild (Grade 1) to moderate (Grade 2) in severity and resolved upon discontinuation of remdesivir. Transaminase elevations have also been reported in patients with COVID-19 who received remdesivir.

Coadministration of remdesivir and chloroquine phosphate or hydroxychloroquine sulfate is not recommended based on cell culture data demonstrating an antagonistic effect of chloroquine on the intracellular metabolic activation and antiviral activity of remdesivir.

In ACTT-1, the collection of adverse event data in this trial was limited to severe (Grade 3) or potentially life-threatening (Grade 4) adverse events, serious adverse events, adverse events leading to study drug discontinuation, and moderate (Grade 2) severity or higher hypersensitivity reactions. Rates of adverse reactions (\geq Grade 3), serious adverse reactions, and adverse reactions leading to treatment discontinuation are presented in [Table 3](#).

Table 3. Summary of Adverse Reaction Rates in Subjects with Mild, Moderate, or Severe COVID-19 in ACTT-1

| Types of Adverse Reactions | Remdesivir N=532 n (%) | Placebo N=516 n (%) |
|--|------------------------|---------------------|
| Adverse reactions, Grades ≥ 3 | 41 (8%) | 46 (9%) |
| Serious adverse reactions | 2 (0.4%) ^a | 3 (0.6%) |
| Adverse reactions leading to treatment discontinuation | 11 (2%) ^b | 15 (3%) |

a Seizure (n=1), infusion-related reaction (n=1).

b. Seizure (n=1), infusion-related reaction (n=1), transaminases increased (n=3), ALT increased and AST increased (n=1), GFR decreased (n=2), acute kidney injury (n=3).

Remdesivir is a substrate for CYP2C8, CYP2D6, and CYP3A4. However, coadministration with inhibitors of these CYP isoforms is unlikely to markedly increase remdesivir levels, as its metabolism is likely to be predominantly mediated by hydrolase activity. See package insert, and additional product related information for full discussion of clinical experience and risks.

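### ACTT-3 and ACTT-4 plan to present adverse events leading to discontinuation, but their capture rules leave out non-serious lower-grade events that can stop study product

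*Protocol*

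**What the plan says.** **Planned output.** Appendix C 9.4.5 and Appendix D 9.4.4 carry the same sentence: "Adverse events leading to premature discontinuation from the study intervention and serious AEs will be presented either in a table or a listing".

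**What is collected in ACTT-3.** Appendix C 8.3.1: "Only Grade 3 and 4 AEs will be captured in this trial and Grade 2 or higher suspected drug-related hypersensitivity reactions". Section 8.3.5 adds serious events of any grade: "all Grade 3 and 4 AEs, and all SAEs occurring from the time the first study product is initially given on Day 1". Required safety laboratory results of every grade go into the database, but "the Grade 1 and 2 laboratory abnormalities are not expected to be reported as adverse events".

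**What is collected in ACTT-4.** Appendix D 8.3.5 likewise limits capture to Grade 3 and 4 events and all serious events. Section 8.3.1 adds clinically significant suspected drug-related hypersensitivity and any deep vein thrombosis or pulmonary embolism. Section 8.3.5.1 captures a new infection only if it is Grade 3 or 4 or serious.

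**When product may be stopped.** Section 7.1.1 of both appendices: "Study product administration for any given subject may be stopped for SAEs, clinically significant adverse events, severe laboratory abnormalities, or any other medical conditions". The same section lets a subject stop for any reason. Neither route carries a grade threshold.

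**What else is recorded.** Discontinuation or suspension for any reason is a safety measure in Section 3 of both appendices, and Section 7.1.1 puts the reason for discontinuation on the case report form.

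**The concern.** The output asks for a class of events that the collection rule does not fully gather. Where stopping is allowed at any grade but reporting mostly starts at Grade 3, the output is truncated by design, and a reader of the results would not know it.

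What is at stake is how tolerability is described. Low-grade reactions that a subject or investigator finds intolerable are what such a table is normally meant to show. For interferon, Appendix C 2.2.3.1 names the reactions that most often called for clinical intervention in a multiple sclerosis trial: "injection site reactions, influenza-like symptoms, depression, and elevation of liver enzymes". Several of these can occur below Grade 3.

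The protocol also shows that the class can be collected separately. Appendix D 2.2.2.1 describes adverse event collection in ACTT-1 as covering Grade 3 and 4 events together with "serious adverse events, adverse events leading to study drug discontinuation, and moderate (Grade 2) severity or higher hypersensitivity reactions".

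**Working it through.** No figure in the plan needs reproducing. The check is whether each kind of event that may stop product also produces an adverse event record.

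| Event that stops product | Adverse event record required? | Counted as a discontinuation, with reason? |
|---|---|---|
| Any serious event | Yes (8.3.5, C and D) | Yes |
| Non-serious, Grade 3 or 4 | Yes (8.3.5, C and D) | Yes |
| Suspected drug-related hypersensitivity | Yes, from Grade 2 in ACTT-3; if clinically significant in ACTT-4 (8.3.1) | Yes |
| Deep vein thrombosis or pulmonary embolism, ACTT-4 | Yes, whatever the grade (D 8.3.1) | Yes |
| Grade 1 or 2 value on a required safety test | Value stored, but not as an adverse event (8.3.1, C and D) | Yes |
| Any other non-serious Grade 1 or 2 event | No | Yes |
| Confirmed systemic fungal infection, non-serious and below Grade 3, ACTT-4 | No (D 8.3.5.1) | Yes |

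1. The last three rows are the gap. Section 7.1.1 permits stopping in all of them. In the fungal row, Appendix D 7.1.1.2 requires both blinded products to stop, with no grade attached.
2. ACTT-4 shows that the two can be aligned. Venous thromboembolism is a halting event in 7.1.1.2 and reportable at any grade in 8.3.1. Systemic fungal infection is a halting event without a matching reporting item.
3. A reason on the case report form is not a substitute. Under 8.3.5.1 an adverse event carries dates, severity, relation to study product, action taken and outcome, and under the safety analysis sections it is MedDRA-coded. No such content is specified for the discontinuation reason.
4. The any-reason measure does not supply the cause. In Appendix D Section 3 the endpoint is incidence and number of discontinuations or suspensions. In Appendix C Section 3 the measure appears among the objectives, but the matching endpoint cell lists only serious events, Grade 3 and 4 events and laboratory values.
5. The size cannot be computed. The protocol gives no rate of low-grade events, and no rate of stopping because of them, for either stage. The nearest figures are ACTT-1 adverse reactions leading to discontinuation (Appendix D Table 3): 11/532 = 2.1% on remdesivir and 15/516 = 2.9% on placebo. They concern another product, and since ACTT-1 is described as collecting such events as their own class, they are not shown to be limited to Grade 3 or higher. They cannot serve as a baseline for what ACTT-3 would capture.
6. The extra reporting load can be scaled but not estimated. Each 1% of subjects with a newly reportable event adds about 0.01 × 923 = 9 forms in ACTT-3 and 0.01 × 1500 = 15 in ACTT-4.

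**The case against.** **The output may mean captured events only.** The safety analysis sections open by naming death, serious events and Grade 3 and 4 events as the endpoints, so the discontinuation output can be read as a subset of these. The grade limit is a deliberate choice in a population with many background symptoms. This is a fair reading and the reason a label alone would be an acceptable minimum. It does not remove the point: the sentence does not state the limit, and the stopping provisions do not share it.

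**Tolerability is measured elsewhere.** Discontinuation for any reason is compared between arms and the reason is recorded. That stands. Low-grade stoppages are counted; what is lost is their description as adverse events.

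**Stronger readings that the protocol does not support.**

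- A reader might infer that low-grade interferon reactions are the events most likely to stop the injections. Appendix C 2.2.3.1 gives no grades, describes two years of dosing three times a week, and pools discontinuation with dose adjustment and added medication. ACTT-3 plans four doses, and 6.1.2 responds to an injection-site reaction by using another site.
- A reader might infer that the table is biased towards no difference between arms, or that a given share of interferon-arm events is missing. Any such percentage only restates the rates assumed for it.
- A reader might infer that ACTT-3 removed a collection class that ACTT-1 had. The ACTT-1 appendix is no longer in this document, the ACTT-1 rule survives as one background sentence, and the common platform rules (main protocol 8.2.1 and 8.2.5) contain no such class.
- Seizure, a halting event in Appendix C 7.1.1.2, might look like another gap. Section 8.3.2 cites convulsions as an example of an event that may be judged serious, and every serious event is captured.

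**Conclusion.** The mismatch holds for both stages, as a modest reporting gap. A non-serious lower-grade event outside the named exceptions can end dosing, and be counted as a discontinuation with a reason, without appearing in the output on adverse events leading to discontinuation. The conclusion rests on the collection and stopping text alone and needs no assumed rate. Neither the number of missing events nor any imbalance between arms can be derived. No decision rule, primary analysis or sample size depends on it. It belongs in the protocol because the analysis plan cannot tabulate events that sites were never asked to report.

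**What to change.** In 8.3.1 of Appendices C and D, add one item to the list of additionally reportable events: *any adverse event, of any grade, that leads to permanent discontinuation of a study product*. Match the wording in 8.3.5 of both appendices, and in Appendix D 8.3.5.1 for infections. Present the output of Appendix C 9.4.5 and Appendix D 9.4.4 for all grades. This is a change to reporting only and leaves the stopping provisions as they are. Limiting the item to permanent discontinuation keeps it to what the planned output covers; temporary holds need not be included.

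If collection is not changed, the minimum is to label the output as restricted to captured adverse events and to place beside it a by-arm summary of the discontinuation reasons already on the case report form.

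Cost: a small number of extra adverse event forms, on the per-1% scaling shown above. No added visits, samples or subjects.

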9.4.6 Baseline Descriptive Statistics

Baseline characteristics will be summarized by treatment arm. For continuous measures the mean, median, minimum, maximum and standard deviation will be summarized. Categorical variables will be described by the proportion in each category (with the corresponding sample size numbers).

9.4.7 Planned Interim and Early Analyses

A DSMB will monitor ongoing results to ensure subject well-being and safety as well as study integrity. The DSMB will be asked to recommend early termination or modification only when there is clear and substantial evidence of a treatment difference. More details about the interim analyses are described in [section 9.4.6.1](#) and [9.4.6.2](#) below as well as a separate guidance document for the DSMB.

On September 4, 2020, the DSMB met for an interim safety review of ACTT-3 data, and they recommended that DMID close further enrollment to patients with a baseline ordinal score of 6. Given that there are multiple clinical trials evaluating interferon beta for the treatment of COVID-19 worldwide, a public announcement describing the change in enrollment was made to inform the scientific community. If necessary, there may be an early evaluation of safety outcomes for the category 6 subjects enrolled in ACTT-3. Specifically, after study Day 29, for all subjects enrolled at an ordinal score of 6, those subjects only may be unblinded and an interim analysis may occur. This could be done if needed in order to determine the risk in this group of patients and convey this risk to other sponsors who can then use this information to make modifications if needed to their ongoing studies. This would be followed by a full analysis after the final data cleaning. The SAP has been modified to describe this interim analysis as well as a revised analysis for the ordinal 6 category.

9.4.7.1 Interim Safety Analyses

Safety analyses will evaluate Grade 3 and 4 AE and SAEs by treatment arm. Safety monitoring will be ongoing with the DSMB reviewing safety data approximately every two weeks during the study. The unblinded statistical team will prepare these reports for review by the DSMB.

9.4.7.2 Interim Efficacy Review

The Lan-DeMets spending function analog of the O'Brien-Fleming boundaries will be used to monitor the primary endpoint as a guide for the DSMB for an overall two-sided type-I error rate of 0.05. Interim efficacy analyses will be conducted at approximately 50% and 100% of total information.

Conditional power will be presented as an additional guide to the DSMB. Conditional power allows computation of the probability of obtaining a statistically significant result by the end of the trial given the data accumulated thus far, incorporating and assuming a hypothesized treatment effect (e.g., the treatment effect assumed for sample size determination) thereafter. If conditional power is less than 20% under the original trial assumptions, consideration should be given to stopping the trial.

The unblinded statistical team will prepare these closed reports for DSMB review and recommendations. Analyses will be presented with blinded codes for treatment arms to protect against the possibility that the DSMB report may fall into the wrong hands. A DSMB charter will further describe procedures and membership.

9.4.8 Sub-Group Analyses

Subgroup analyses for the primary outcomes will evaluate the treatment effect across the following subgroups: geographic region, duration of symptoms prior to enrollment, baseline disease severity (ordinal scale), age, race, ethnicity, sex, and comorbidities. A forest plot will display confidence intervals across subgroups. Interaction tests will be conducted to determine whether the effect of treatment varies by subgroup.

9.4.9 Exploratory Analyses

10. SUPPORTING DOCUMENTATION AND OPERATIONAL CONSIDERATIONS – ALL STAGES

All supporting documentation and operational considerations are applicable to the entire platform trial and are not unique to the individual stages. These are therefore covered in the main protocol document.

APPENDIX D - ACTT-4: BARICITINIB/REMDESIVIR Vs. DEXAMETHASONE/REMDESIVIR

1. PROTOCOL SUMMARY

1.1 ACTT-4 – Synopsis

Study overview

Severe COVID-19 is marked by a hyperinflammatory state characterized by upregulation of multiple cytokines. Multiple therapeutic strategies have been proposed to counter this inflammatory phase. To date, only two anti-inflammatory medications have demonstrated efficacy in large randomized trials – dexamethasone and baricitinib.

In the Randomized Evaluation of Covid-19 Therapy (RECOVERY) trial, treatment with dexamethasone demonstrated a lower mortality rate, 22.9% in the dexamethasone group versus 25.7% in the usual care group (absolute difference 2.8%; $p<0.001$).⁽¹⁵⁾ In ACTT-2, treatment with baricitinib in addition to remdesivir demonstrated a shorter median time-to-recovery of 7 days versus 8 days with remdesivir alone [rate ratio for recovery 1.16, $P=0.03$] and a lower 28-day mortality of 5.1% and 7.8% in the combination and control arms, respectively (absolute difference 2.7%; $P>0.05$). (Kalil et al, 2020)

These two studies, however, are very different – different study populations, different baseline mortality rates, and different data collected. Only ACTT-2 was blinded, and only in ACTT-2 was the anti-inflammatory intervention given in addition to an antiviral. Therefore direct comparison of these studies to determine which interventions are of value in which populations is difficult. ACTT-4 will evaluate adult patients hospitalized with COVID-19 and requiring supplemental oxygen by low flow, high flow or non-invasive mechanical ventilation modalities to determine if baricitinib or dexamethasone in combination with remdesivir are more effective at preventing progression to mechanical ventilation or death (among other outcomes) or if they are similar.

Enrollment Period:

It is anticipated the enrollment will be completed in 3-4 months.

General

ACTT-4 will evaluate the combination of baricitinib and remdesivir compared to dexamethasone and remdesivir in adult patients hospitalized with COVID-19 and requiring supplemental oxygen. Subjects will be assessed daily while hospitalized. If the subjects are discharged from the hospital, they will have a study visit at Days 15, 22, and 29. For discharged subjects, it is preferred that the Day 15 and 29 visits are in person to obtain safety laboratory tests, OP swabs, plasma (Day 29), and serum for secondary research as well as clinical outcome data. However, if infection control or other restrictions limit the ability of the subject to return to the clinic, these visits may be conducted by phone and only clinical data will be obtained. The Day 22 visit does not have laboratory tests or collection of samples and is conducted by phone. Additionally, in

